All (serious) adverse events or (serious) adverse device effects will be documented on the appropriate “Adverse event/Adverse device effect form.” Safety parameters of this clinical trial are predominantly based on the documentation of adverse events, serious or non-serious, as well as expected and unexpected reactions. Also, near incidents will be reported.

SUBJECT POPULATION AND SAMPLE SIZE

Subjects in the study will be recruited within the UNC School of Dentistry Predoctoral and Graduate clinics. Up to 50 adult subjects (18 years of age and older) will be recruited to provide at least 50 sets of matched or unmatched paired teeth in need of study restorations. Fifty restorations available at baseline and 40 at the 18-month follow-up visit are the minimum number recommended in the 2001 ADA guidelines for clinical trials on resin-based composite resins for posterior restorations. Subjects will be in need of two or four medium-sized Class II restorations in molar and/or premolar teeth.

INCLUSION AND EXCLUSION CRITERIA

To be included in the study, a potential subject must satisfy the criteria described below and be available for the various follow-up visits. A record will be maintained of the reasons for the loss of subjects from the study.

Inclusion Criteria

To be considered for inclusion in the study, subjects must:

- Be older than 18 years of age.
- Have a pair of similar lesions or failed restorations in vital permanent molar or premolar teeth requiring Class II restorations of moderate size that extend between one-quarter and one-third of the way up one or more of the cuspal slopes. Any Class II restoration must have a proximal portion with at least one margin that obviously extends into an interproximal embrasure. (Note: A tooth will be considered vital for the purposes of the study if it is clinically and/or radiographically free of any signs and symptoms of periapical pathology and responds to routine vitality testing.)
- Be capable of giving written informed consent.

Exclusion Criteria

Subjects will be excluded from participating in the study if they:

- Have a history of any adverse reaction to clinical materials of the types to be evaluated.
- Have a medical or dental history that could possibly complicate the provision of the proposed restorations and/or influence the behavior and performance of the restorations in clinical service.
- Have advanced periodontitis affecting the mobility of the teeth.

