- Have xerostomia caused by medications, Sjögren's syndrome, etc.
- Are individuals with special needs.

Distribution of restorations

Each subject shall have a minimum of one pair and a maximum of two pairs of permanent molar or premolar teeth requiring moderate sized Class II restorations. No tooth shall require more than one restoration. Sufficient subjects will be recruited to ensure 50 pairs of test and control study restorations are placed. Although desirable, the pairs are not required to be precisely matched. For example, for purposes of the study, paired restorations can be placed in teeth #15 and #31 (upper left second molar and lower right second molar).

All teeth and restorations in the study will have occlusal contacts. All restorations, with the exception of disto-occlusal restorations in the most distal molars, will have a proximal contact with the adjacent tooth. No two test restorations of either material will be in occlusal or proximal contact with each other.

Selection of Teeth

In addition to the above criteria, the following will apply in tooth selection:

- The tooth must be vital, as determined by thermal test (Hygenic Endo-Ice, Coltène/Whaledent AG).
- The tooth must be of typical size, appearance and morphology.
- The tooth must share, where appropriate, sound proximal contacts with adjacent teeth.
- The tooth must be free of cracks and other defects and lesions necessitating operative intervention other than the restoration to be undertaken as part of the study.
- Proper isolation must be possible.

MATERIALS

The test material is Filtek™ Bulk Fill Posterior Restorative, a bulk fill, low-shrink, light-cured, radiopaque composite resin restorative indicated for use in direct posterior situations. The control material is Filtek™ Supreme Ultra Universal Restorative, a conventional composite resin. Restorations will be bonded with Scotchbond Universal Adhesive.

Manufacturers' instructions for use will be followed for all restoration placements included in the study. Manufacturers' instructions for use for Filtek™ Supreme Ultra Universal Restorative and Filtek™ Bulk Fill Posterior Restorative, and Scotchbond Universal Adhesive are given in the Investigator's Brochure.

PRE-OPERATIVE PROCEDURES

In the screening visit, written informed consent will be obtained from each subject. Each subject will be allowed to ask questions concerning the evaluation and to consider the answers given before signing the consent form.

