The pre-operative status and a periapical radiograph (where clinically indicated) of each tooth to be included in the study will be evaluated and a pre-treatment status form will be completed (Patient Registration Form). The condition of the gingival tissue adjacent to each tooth to be restored will be assessed (four sites: facial, lingual, mesial and distal) and recorded as pre-treatment measurements (Patient Registration Form). Oral hygiene status including plaque index will be determined after periodontal evaluation. Appropriate vitality and radiographic assessments will be completed where indicated clinically, and will be recorded. A pre-operative photographic record will be made.

The restorative material to be used will be allocated by means of a randomization scheme based on computer generated random numbers (Appendix 1). Before starting the study, the PI will decide, by means of a toss of a coin, whether even or odd numbers indicate the test or control treatment. For each set of paired teeth, the lowest numbered tooth (Universal Numbering System) will be selected first. Before cavity preparation, the first randomization number in the sequence will be noted and the allocated treatment procedure carried out as indicated by the random number obtained. The second cavity is then prepared and restored using the second treatment option (next number in the row). Restorative treatments will be randomly assigned to the study teeth at the same visit at which pre-treatment gingival condition, vitality, etc., are determined.

The treating clinician will complete the preparation and placement of restorations, and the arrangements for the subsequent follow-up of the patients.

OPERATIVE PROCEDURES

Local anesthesia will be administered unless declined by the patient. The teeth to be restored will be prepared using conventional instruments and techniques, and no bevels will be placed on any of the cavosurface margins. Shades will be selected before the procedure is started and the tooth is still moist. Rubber dam will be used.

A sectional metal matrix (Garrison Dental or similar) and bitine ring will be placed along with plastic or wooden wedges. At the operator's discretion (e.g., if the preparation is

too wide for a sectional matrix), a thin circumferential metal matrix (Convexi-T, Clinician's Choice or similar) may be used. The bonding system will be used in the selective etch mode according to manufacturer's instructions.

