All restorations carried out in this study will be at no cost to the subjects. Subjects will be expected to attend the one-, two-, three-, and five-year follow up visits. Compensation of \$50 will be paid to each subject at baseline and each follow-up visit (total of \$250).

MONITORING

The study will be monitored at appropriate intervals by [name], Scientific Affairs Manager, 3M ESPE Dental Products, [name] [[contact]], or his designee, by means of regular contact to evaluate study data and photographs.

DATABASE MANAGEMENT

Each subject recruited into the study will be given a unique identifying code number and the subject's identity will be kept confidential as far as is practical.

ANALYSIS OF THE RESULTS

The demographic and baseline measurements, and the study data obtained, will be analyzed by means of tables of percentages to summarize the characteristics of the patients and the baseline data. Tables of percentages will be prepared to illustrate the follow-up and retrospective analysis findings. Cross tabulation will be prepared as necessary.

Statistical analyses

Chi-square (χ^2), McNemar and Mann-Whitney-U tests will be applied as appropriate to compare the baseline and follow-up/review findings regarding the two types of restorations.

PROBLEM CASES

In the case of an experimental Filtek™ Bulk Fill Posterior Restorative or Filtek™ Supreme Ultra Universal Restorative composite resin restoration being found to have failed or to be clinically unsatisfactory on review, the investigator will:

- Complete the failed restoration form.
- Make a photographic and silicone impression record of the failed restoration.
- Make arrangements to replace or, if appropriate, repair the restoration.

Replacements of failed restorations will not form part of the study.

In the case of failure of restorations placed using either restorative system, the tooth will be re-restored at no cost to the subject or investigator. The contact person at 3M ESPE ([name], [contact]) should be notified before this treatment is done.

ADVERSE EVENTS

If an adverse event occurs any decision as to whether to prematurely stop the study will be taken jointly by the PI, 3M ESPE, and IRB. Changes to the protocol will be by arrangement between the PI, IRB, and 3M ESPE, and will take the form of a signed amendment.

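### Subjects may give two pairs, but the listed tests treat pairs or restorations as independent, so p-values and any intervals can be wrong where the material difference varies between subjects

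*Combined protocol and SAP*

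**What the plan says.** Under Distribution of restorations: "Each subject shall have a minimum of one pair and a maximum of two pairs of permanent molar or premolar teeth". Subject Population and Sample Size agrees: "Subjects will be in need of two or four medium-sized Class II restorations in molar and/or premolar teeth".

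The target is set in pairs: "Sufficient subjects will be recruited to ensure 50 pairs of test and control study restorations are placed". The number of subjects has a ceiling but no floor: "Up to 50 adult subjects (18 years of age and older) will be recruited to provide at least 50 sets of matched or unmatched paired" […]. No limit is placed on how many subjects may give two pairs. The only rationale for the size counts restorations: "Fifty restorations available at baseline and 40 at the 18-month follow-up visit are the minimum number recommended in the 2001 ADA guidelines".

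Each pair holds one tooth per material, and the Pre-operative Procedures section allocates pair by pair.

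The Statistical analyses paragraph is a single sentence. It names chi-square and then says that "McNemar and Mann-Whitney-U tests will be applied as appropriate to compare the baseline and follow-up/review findings regarding the two types of restorations". It does not say which test serves which comparison, does not name a unit of analysis, and gives no method for a subject who contributes more than one pair. No other section supplies one.

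**The concern.** Two pairs in one mouth are not two independent replicates of the comparison if people differ in how the two materials perform relative to each other. A heavy grinder, for example, might wear one material faster than the other in both pairs. An analysis that counts those pairs as independent then credits the trial with more information than it has.

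This is a separate matter from pairing test with control. McNemar respects that pairing but ignores that two pairs may share a mouth. Chi-square and Mann-Whitney U ignore both and treat up to four restorations in a mouth as unrelated. Leaving the choice of test to the analyst does not help, because none of the three takes account of the subject.

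The hypothesis is that the materials perform similarly. Such a claim rests on how large a difference the data can exclude, so an interval that is too narrow favours the conclusion the trial hopes to reach.

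**Working it through.** **Inputs from the protocol.** 50 pairs; one or two pairs per subject; at most 50 subjects; allocation within each pair; three listed tests.

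**Not in the protocol, so assumed.** Two-sided alpha of 5%; correlation ρ of 0.1 to 0.5 between the two test-minus-control differences of a two-pair subject; event and discordance rates as stated at each step. The protocol gives no power, margin or correlation, so 50 pairs cannot be re-derived from its own inputs.

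**Number of subjects.** 50 / 2 = 25 at the least and 50 / 1 = 50 at the most.

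**Design effect for the paired difference.** Let k subjects give two pairs and 50 − 2k give one. Then DE = 1 + ρ(Σm²/50 − 1), where m is the number of pairs per subject. Since Σm² = 4k + (50 − 2k) = 50 + 2k, DE = 1 + ρ(2k/50). Effective pairs are 50/DE, and the coverage of a nominal 95% interval is 2Φ(1.96/√DE) − 1.

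| Two-pair subjects (all subjects) | ρ | DE | Effective pairs | Coverage |
|---|---|---|---|---|
| 25 (25) | 0.1 | 1.10 | 45.5 | 93.8% |
| 25 (25) | 0.3 | 1.30 | 38.5 | 91.4% |
| 25 (25) | 0.5 | 1.50 | 33.3 | 89.0% |
| 12 (38) | 0.1 | 1.05 | 47.7 | 94.4% |
| 12 (38) | 0.3 | 1.14 | 43.7 | 93.3% |
| 12 (38) | 0.5 | 1.24 | 40.3 | 92.2% |
| 5 (45) | 0.3 | 1.06 | 47.2 | 94.3% |
| 0 (50) | any | 1.00 | 50 | 95.0% |

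The splits with 12 and 5 two-pair subjects are illustrations; the protocol gives no expected split.

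**In percentage points.** With an assumed 10% of pairs discordant and no mean difference, the half-width is 1.96 × √(0.10/50 × DE). Treating pairs as independent gives 8.8 points. With 25 two-pair subjects the correct value is 10.0 at ρ = 0.3 and 10.7 at ρ = 0.5.

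**Simulated error of nominal 5% tests.** 25 subjects with two pairs each, 40,000 trials per scenario, 20% event probability in a typical subject, no average difference between materials.

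- McNemar, uncorrected: 4.4% to 5.0% when subjects differ only in overall risk or not at all. With subject-by-material variation it is 6.1%, 8.2% and 11.8% at correlations of the two differences of about 0.08, 0.25 and 0.52.
- Unpaired chi-square: 3.5% and 1.3% when test and control teeth in a mouth correlate at 0.14 and 0.38 and there is no subject-by-material variation; 8.0% and 14.8% when that variation is large.
- t-test on one mean difference per subject: 5.0% to 5.5% throughout.

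**The case against.** Several objections have force.

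- **Shared mouth factors cancel.** Diet, bite force and caries risk act on both teeth of a pair, so their main effects largely drop out of the paired difference. This stands. A reader might infer that shared risk alone makes McNemar too liberal; the simulation shows that it does not. Because pairs are allocated separately, McNemar also keeps its size if the materials are identical in every mouth. Only variation in the material difference between subjects does harm.
- **The plan promises no interval.** It offers percentage tables and three tests. This stands: a reader might infer that a stated precision is wrong, but none is stated. The coverage figures apply only if an interval is reported to support similarity.
- **25 subjects is the floor.** This stands. A reader might infer that 50 pairs carry the information of 25; that needs two pairs from every subject and ρ = 1.
- **Error bars are not always too narrow.** This stands for the unpaired tests, which are conservative when the two teeth in a mouth resemble each other and liberal when subject-by-material variation is large.
- **The version of McNemar matters.** With 25 two-pair subjects and 10% discordant pairs, exact McNemar rejects about 1% to 3% of the time at ρ of 0.1 to 0.5, while the uncorrected test rejects about 6% to 10%. At 20% discordance and ρ = 0.5 the exact test reaches about 6%. So the size of the effect depends on a choice the plan leaves open. The conservatism of an exact test with few discordant pairs does not repair an interval.

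None of this supplies a listed method that handles two pairs in one subject.

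**Conclusion.** The point holds in a conditional form. The protocol permits one or two pairs per subject and names no test that allows for it. In the worst case of 25 two-pair subjects, with an assumed correlation of differences of 0.1 to 0.5, the loss is moderate: a standard error too small by a factor of √1.1 = 1.05 to √1.5 = 1.22. It falls in proportion to the share of two-pair subjects and vanishes with one pair each.

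The omission is certain; its size is not, since the documents give neither the correlation nor the split of subjects. They do not support the broader reading that the comparison is necessarily too precise. It is worth correcting because a similarity claim leans on interval width and no power calculation is given that could absorb the loss.

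**What to change.** In the Statistical analyses paragraph, replace the independence-based tests for the test-versus-control comparison with paired methods that take the subject as the cluster:

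- Binary criteria (acceptable versus unacceptable): a clustered McNemar test, with a subject-clustered interval for the difference.
- Ordinal FDI scores and wear: a clustered signed-rank test, or a bootstrap or permutation that resamples or flips whole subjects, so that both pairs of a mouth move together.
- If robust variance is used, a small-sample correction, because there are only 25 to 50 clusters and discordant pairs may be few.
- Every table: the number of subjects beside the number of pairs, and how many subjects gave two.

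The cost is wording and a little programming. Recruitment, procedures and data collection do not change. Intervals may widen slightly. Reducing each subject to one averaged value would be simpler, but it weights subjects rather than pairs and treats ordinal scores as interval data, so the plan should say which weighting it intends.

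### Pairs may join teeth of different arch or type, but the planned tests use neither factor: removable noise in the test-control contrast, not bias

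*Combined protocol and SAP*

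**What the plan says.** **Pairing.** The sample size section of the protocol seeks "at least 50 sets of matched or unmatched paired teeth in need of study restorations" and adds: "Subjects will be in need of two or four medium-sized Class II restorations in molar and/or premolar teeth". The section on distribution of restorations states "Although desirable, the pairs are not required to be precisely matched" and illustrates this: "paired restorations can be placed in teeth #15 and #31 (upper left second molar and lower right second molar"). That example crosses arches but keeps tooth type the same. No example shows a molar with a premolar, but nothing excludes it. The inclusion criterion asks that subjects "Have a pair of similar lesions or failed restorations in vital permanent molar or premolar teeth"; this concerns the lesion, not the tooth's type or position.

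**Allocation.** Under Pre-operative Procedures, "the lowest numbered tooth (Universal Numbering System) will be selected first". A random number fixes its material and the other tooth receives the other material. There is no stratification by tooth type or arch.

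**Size.** "Sufficient subjects will be recruited to ensure 50 pairs of test and control study restorations are placed". The figure of 50 rests on a guideline minimum; no power, effect size or margin is stated. A subject may contribute one or two pairs.

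**Analysis.** Under Statistical analyses, after naming chi-square, the protocol says "McNemar and Mann-Whitney-U tests will be applied as appropriate to compare the baseline and follow-up/review findings". Tables of percentages and cross tabulations are also planned, but no table, model, stratum or sensitivity analysis is tied to tooth type or arch.

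**The concern.** If wear or another outcome differs between molars and premolars, or between arches, that difference enters the test-minus-control difference of every mixed pair. Its sign is positive or negative according to which tooth received which material. None of the listed tests takes a covariate, so the component stays in the contrast.

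Precision matters more than usual here. The hypothesis is similar performance, there is no margin, and the number of pairs was not derived from a power calculation. Avoidable noise makes a non-significant result more likely, and such a result is easily read as similarity. Wear resistance is named first in the hypothesis, and measured wear is the kind of outcome for which a covariate model is straightforward.

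**Working it through.** The 50 pairs cannot be reproduced, because the protocol gives no alpha, power, effect size, SD, event rate or margin. The checks below use 50 pairs and within-pair randomisation from the protocol; everything else is an assumption.

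**1. Variance of the paired difference.** Let s be the residual SD of one tooth within a pair, d the tooth-type or arch difference in units of s, and f the share of mixed pairs. In a mixed pair the tooth difference enters as +d or -d with equal probability. Then, in units of s²:

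Var(difference) = 2 + f·d², so the inflation factor is 1 + f·d²/2, and 50 pairs are worth 50/(1 + f·d²/2).

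| f | d = 0.25 | d = 0.5 | d = 1.0 |
|---|---|---|---|
| 0.3 | 1.009 (49.5 pairs) | 1.038 (48.2) | 1.15 (43.5) |
| 0.5 | 1.016 (49.2) | 1.063 (47.1) | 1.25 (40.0) |
| 1.0 | 1.031 (48.5) | 1.125 (44.4) | 1.50 (33.3) |

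**2. Power for a continuous outcome such as wear.** Assume a true material difference of 0.5 s and a two-sided 0.05 test. Power = Φ(0.5/√((2 + f·d²)/50) − 1.96).
- Tooth effect removed completely: 0.5/√(2/50) = 2.5, and Φ(0.54) = 70.5%. This treats the tooth effect as known, so it is a best case.
- Not removed, all pairs mixed: 69.2% at d = 0.25, 65.4% at d = 0.5, 53.2% at d = 1.0.
- Not removed, half the pairs mixed: 60.9% at d = 1.0.

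**3. Chance imbalance is the same quantity.** Take 20 mixed pairs of 50 (f = 0.4) and d = 1. The residual part of the squared standard error is 2/50 = 0.040. The imbalance part is m·d²/50² = 20/2500 = 0.008. The total is 0.048, so the unadjusted standard error is 0.219 s against 0.200 s after adjustment. The ratio 0.048/0.040 = 1.20 equals 1 + 0.4/2, the factor in step 1. A surplus of six teeth of one kind under one material would shift the mean by 6/50 = 0.12 s, about half of the 0.219 s standard error. The expected shift is zero.

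**4. How likely is that surplus?** With independent allocation, P(|2X − 20| ≥ 6), X ~ Bin(20, 0.5), is 0.263. But the Appendix 1 list, taken in couples along its rows, starts with an even number in 25 of the first 50 couples and an odd number in 25. Upper teeth carry the lower numbers in the Universal system, as in the protocol's example, so in a cross-arch pair the first-treated tooth is the upper one. With 50 pairs allocated in that order, and 20 cross-arch pairs falling at random among them, the split is hypergeometric and the probability is 0.148. It is also 0.148 for 30 such pairs and zero if all 50 are cross-arch. For molar-premolar pairs the lower number can belong to either type, so the list gives no comparable assurance.

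**5. McNemar outcomes.** The exact test was simulated with 50 pairs, 4,000 runs per setting and assumed failure rates by tooth type. All-mixed pairs were compared with like-with-like pairs.

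| Assumed rates | Type I error, all mixed | Power at odds ratio 3, like-with-like | Power, all mixed |
|---|---|---|---|
| 5% and 15% | 0.019 | 0.38 | 0.34 |
| 20% and 40% | 0.027 | 0.65 | 0.61 |

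The type I error stays below 0.05, and power falls by about 0.04 even when every pair is mixed.

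**The case against.** A reader might infer that loosely matched pairs bias the comparison of materials or invalidate the planned tests. The documents do not support that. Material is randomised within each pair, the expected shift is zero, and the unadjusted standard error already contains the chance imbalance. Counting imbalance as a further harm on top of the extra variance would count it twice. Leaving out a prognostic factor in a randomised within-pair comparison costs efficiency, not validity.

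The protocol also limits tooth differences. It requires similar, moderate-sized lesions, occlusal contact, proximal contact with one exception, typical tooth size and morphology, feasible isolation, and rubber dam. In Table 1, wear is rated against corresponding enamel and periodontal response against a reference tooth. These controls are real and argue for the lower part of the assumed range of d. They do not equalise arch or tooth type, and the protocol does not say that the impression-based or digital wear measurements are scaled to enamel.

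Finally, covariate-adjusted ordinal models for 16 rated properties at four reviews, with about 50 pairs and probably sparse categories, may not fit. That stands, and it is why the model is proposed for measured wear only.

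**Conclusion.** The point holds as a modest and avoidable loss of precision, and the change is an optional refinement. Cross-arch pairing is explicit and molar-premolar pairing is permitted by implication. No planned test uses either factor.

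For a tooth difference of 0.25 to 1.0 per-tooth SD, the variance of the paired difference rises by about 1% to 25% with 30% to 50% of pairs mixed. The 50% figure needs every pair mixed and a difference of 1 SD; it should not be read as the expected loss. For McNemar outcomes the loss is small throughout. Both the share of mixed pairs and the tooth effect are assumptions. If mixed pairs are few or the effect is small, adjustment gains almost nothing.

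That chi-square and Mann-Whitney U ignore the pairing altogether is a separate matter and is not counted in these figures.

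**What to change.** In the Statistical analyses section, specify before results are seen:

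- **Measured wear:** a within-pair mixed model with material, tooth type (molar or premolar) and arch (upper or lower) as fixed effects, and pair and subject as random effects. The subject term is needed because a subject may contribute two pairs.
- **Clinical (FDI) scores and acceptable/unacceptable outcomes:** a paired test without covariates, with McNemar for the binary outcomes. Repeat it in same-type, same-arch pairs as a sensitivity analysis. That subset is smaller, so read it for consistency of the estimate rather than for significance.
- **Description:** a table of tooth type and arch by material, with the number of mixed pairs, so that any imbalance is visible.

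No new data are needed: tooth number must be known in order to allocate, and type and arch follow from it. The cost is two degrees of freedom in the wear model and a little more analysis work.

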The aim of this randomized, controlled clinical investigation is to evaluate the performance of 3M ESPE Filtek™ Bulk Fill Posterior Restorative composite resin in the restoration of moderate-sized Class II cavities in the permanent teeth of adult patients. This material will be compared with Filtek™ Supreme Ultra Universal Restorative (3M ESPE), an established and widely used composite resin restorative material. Restorations performed with both composite resins will be bonded with Scotchbond Universal Adhesive.

[name] of the Department of Operative Dentistry, University of North Carolina (UNC) will be the principal investigator (PI) with overall responsibility for the conduct and reporting of the study. [name] and other Operative Dentistry personnel at UNC will undertake the clinical elements of the study. The study will be of five years duration.

ETHICAL STANDARDS

The study will be conducted in accordance with the Declaration of Helsinki (1964) as revised in Venice in 1983. IRB approval will be obtained prior to commencing the study and written informed consent will be obtained from all patients prior to recruitment into the study. Implicit in giving informed written consent, each patient will reserve the right to withdraw from the study at any time.

RISK ASSESSMENT

Filtek™ Bulk Fill Posterior Restorative is assessed as minimal risk. There is no anticipated clinical benefit of use of Filtek™ Bulk Fill Posterior Restorative over conventional composite resin materials except for the reduced time needed for the restorative procedure.

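### Allocation is read from a number list printed in the protocol, with no concealment step described and no stated rule that eligibility, pairs and pair order are fixed before the number is seen

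*Combined protocol and SAP*

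**What the plan says.** All of the allocation method is in the protocol, mainly under PRE-OPERATIVE PROCEDURES.

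- **List and key.** The numbers are in Appendix 1, which is printed in the protocol. Before the study starts, "the PI will decide, by means of a toss of a coin, whether even or odd numbers indicate the test or control treatment". One key serves the whole study.
- **Use of the list.** In each pair the tooth with the lowest Universal number comes first. "Before cavity preparation, the first randomization number in the sequence will be noted and the allocated treatment procedure carried out". For its partner, "The second cavity is then prepared and restored using the second treatment option (next number in the row".
- **Timing.** The section first has the pre-operative status "of each tooth to be included in the study will be evaluated and a pre-treatment status form will be completed". After describing allocation it adds: "Restorative treatments will be randomly assigned to the study teeth at the same visit at which pre-treatment gingival condition, vitality, etc., are determined". Vitality is an entry criterion under Inclusion Criteria and Selection of Teeth.
- **Forming pairs.** A subject contributes one or two pairs (Distribution of restorations). "Although desirable, the pairs are not required to be precisely matched"; the example given is tooth #15 with tooth #31. One restriction is that "No two test restorations of either material will be in occlusal or proximal contact with each other".
- **Masking.** The only masking described is that of the two examiners under FOLLOW-UP ASSESSMENT.

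The supplied text names no holder of the list or key, and mentions neither envelopes nor central release. It contains no statement that eligibility, pairs and pair order are closed before the number is noted. The Patient Registration Form itself is not in the supplied text.

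**The concern.** Random numbers protect a comparison only while nobody who decides what enters the study knows what comes next. Here the list is open and the key never changes. One observed allocation reveals the key, because the two materials are placed differently (OPERATIVE PROCEDURES: bulk increments up to 5 mm against layers of at most 2 mm). With the reading order and current position also known, later allocations can be read off.

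The open choices are whether a borderline tooth qualifies, which subject or pair takes the next number and, with four teeth, how they are paired. Some entry criteria call for judgement, such as typical morphology, similar lesions and feasible isolation. Pairs may differ in arch and position. If foreknowledge influenced these choices, the two materials would be compared on systematically different teeth. Pairing within a subject does not balance tooth-level factors, and masked examiners cannot undo a selection made before placement.

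**Working it through.** The plan gives no figure to reproduce. The check asks how much a person who knows the next allocations could change.

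**1. Two-tooth subject.** There is one pair and the lowest number goes first, so each allocation gives exactly 1 possible test tooth. No within-subject steering is possible once the two teeth are chosen.

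**2. Four-tooth subject.** Label the teeth 1 < 2 < 3 < 4 by Universal number. Let T or C be the material given to the lower-numbered tooth of a pair; its partner gets the other. There are 6 ways to choose 2 test teeth from 4. The test-tooth sets that can be reached are:

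| Pairing | Next two are T,T | Next two are C,C | Next two differ, pair order free |
|---|---|---|---|
| {1,2} and {3,4} | {1,3} | {2,4} | {1,4} or {2,3} |
| {1,3} and {2,4} | {1,2} | {3,4} | {1,4} or {2,3} |
| {1,4} and {2,3} | {1,2} | {3,4} | {1,3} or {2,4} |
| **Distinct sets, all pairings admissible** | **2** | **2** | **4** |

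- If two pairings are admissible: 1 or 2 sets when allocations agree, 2 or 4 when they differ.
- If one pairing is admissible or recorded, with order free: 1 when they agree, 2 when they differ.
- If pairing and order are both recorded first: 1 in every case.

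**3. How often the next two differ.** Appendix 1 as extracted has 39 rows of 8 numbers, or 39 × 8 / 2 = 156 couples. The text does not say whether successive pairs run along rows or down columns. Comparing the parity of the first number in consecutive couples, over the first 50 couples (49 comparisons):

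- along rows: 30/49 = 61% differ;
- down columns: 29/49 = 59% differ.

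These describe opportunity in two-pair subjects. They do not measure bias.

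**4. Does one number fix both teeth?** Along rows, each of the first 50 couples has one odd and one even number, so the next number in the row always gives the other material. Down columns, three of the first 50 couples have equal parity (69/01, 06/22, 20/82). There the statement holds only if giving the other material takes precedence over the next number.

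**5. Number of four-tooth subjects.** This is not given. SUBJECT POPULATION AND SAMPLE SIZE allows up to 50 subjects and asks for at least 50 pairs. Assuming exactly 50 pairs from N subjects with one or two pairs each, four-tooth subjects = 50 − N. That is 0 for N = 50 and 25 for N = 25.

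**6. What cannot be computed.** The documents give no basis for the number of borderline teeth, the effect of subject order, or the size or direction of any bias.

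**The case against.** The strongest reply is that the design already closes most of the gap. Every pair contributes one tooth to each material, the order within a pair is set by rule, lesions must be similar and of moderate size, study restorations may not touch one another, and examiners are masked. The text also describes assessment and the registration form first, then allocation just before cavity preparation, which suggests that the teeth have been chosen by then. This stands as a limit on reach. The order of description favours assessment first, but the only timing stated is that both fall within one visit, and nothing makes the form a lock.

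Several stronger readings are tempting, and the documents do not support them:

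- **That the person who sets the key also places the restorations.** AIM OF STUDY says "other Operative Dentistry personnel at UNC will undertake the clinical elements of the study", but a name removed from the public copy precedes those words. The unredacted text may settle the matter, so it cannot be counted as an omission.
- **That anyone holding the protocol can read the next allocation.** They also need the key, or one observed allocation to reveal it, together with the reading order and the current position.
- **That 4 of 6 sets, or about 60% differing, indicates a large bias.** The counts show what could be chosen in an unknown number of subjects, possibly none.
- **That steering is likely.** Nothing in the documents shows that it would happen.

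**Conclusion.** The point holds as a gap in allocation safeguards. Following the supplied text leaves an open list with a fixed key, no described concealment, and no stated lock on eligibility, pairs or pair order. Someone with the knowledge set out above could foresee allocations while borderline entry, subject order and, in four-tooth subjects, pairing and pair order are decided.

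The quantifiable part is small. There is no within-subject steering with two teeth, and at most 4 or 2 reachable sets with four. Those maxima assume that all three pairings are admissible and pair order is free. The range of 0 to 25 four-tooth subjects assumes exactly 50 pairs. The conclusion is also limited to the supplied text: the registration form, or a part of the document not available for review, could contain a safeguard. This is a worthwhile, inexpensive improvement and not evidence of a biased comparison.

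**What to change.** 1. **Lock before disclosure.** Add to PRE-OPERATIVE PROCEDURES: *Eligibility of each tooth, the study teeth, the pairs and the order of the pairs are recorded and dated on the Patient Registration Form before any allocation is disclosed.* The order must be included. Recording the pairs alone still leaves 2 reachable sets in a four-tooth subject when the next two allocations differ; recording the order as well leaves 1.
2. **Conceal the list.** Remove Appendix 1 from protocol copies used by treating clinicians. State by role who holds the list and key, and that these people do not place restorations. Release each pair's allocation from sequentially numbered sealed opaque envelopes or on screen.

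Both steps are needed, because the first does not stop a known list from influencing borderline entry or the order of subjects.

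**Cost.** No extra subjects, visits or assessors. Step 1 is one sentence and one dated entry on an existing form. Step 2 takes about 50 envelopes, one per pair, or an on-screen release. It assumes that existing staff who do not place restorations are available, which the documents do not confirm. The downside is minor administration at the placement visit.
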